## Statistical Analysis Plan

A Multi-center Outcomes Clinical Study of the PyroTITAN™ HRA Shoulder Implant in Humeral Head Resurfacing

Number: CP-HRA-002  
ST: ST1159  
Version: 1.0 05/Oct/2023  
Page: 15 of 19

$H_a$  = Alternative hypothesis that the success rate in the investigational group is non-inferior to the reference rate

$\delta$  = Non-inferiority margin pre-specified to be 3.3%.

The survival rate (the clinical success rate) will be calculated and the associated 95% exact confidence interval presented. If the upper 95% confidence limit is greater than the reference rate minus the non-inferiority margin ( $96.1 - 3.3 = 92.8\%$ ) then non-inferiority of the observed rate to the reference rate to within a 3.3% margin can be concluded.

Additionally, survival rate (the clinical success rate) and the associated 95% exact confidence interval at 2 and 5 years will be calculated and presented.

If data allows, time-to-event curves for device survival will be estimated using the Kaplan-Meier technique. For analysis of device survival, those lost to follow up or withdrawn from the study for reasons other than device revision or removal will be regarded as censored observations.

The primary analysis of this endpoint is to be carried out using the FAS population. The same analysis will be carried out on the PP population as supporting analyses.

As an additional analysis, the primary endpoint will be summarised for PP1 and PP2 populations in order to compare the cohort of subjects enrolled after the device changes to the original cohort of subjects.

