# 6 STATISTICAL CONSIDERATIONS

## 6.1 Determination of Sample Size

The following is the sample size justification taken from the study protocol V2, 27-May-2013:

The original sample size in this study was 150 enrolled subjects. Additional proof testing and improvements in the device inspection process were employed during the study, at which time it was determined that an additional cohort of subjects was necessary. We are now comparing a cohort of subjects enrolled after these changes to the original cohort of subjects.

With an expected attrition rate of 10% per annum, this will yield an evaluable sample size of 52 shoulders at ten years ( $150 * 0.9^{10} = 52.3$ , where 0.9 or 90% is the number expected to be retained from one year to the next). Based on past experience, we may obtain clinical follow-up on this number of shoulders, but we may obtain radiographic follow-up on as few as two-thirds of these shoulders (about 35 shoulders). This remaining number of evaluable shoulders with clinical and radiographic follow-up is adequate to establish a reliable ten-year survival estimate of survival for hemi arthroplasty (Dorey and Amstutz, 1986).

For the new cohort, the sample size is calculated based on the non-inferiority of the study device. The success rate for the study device is 96.1% from the original population and is used as reference rate. Therefore, for a conservative success rate of 96.1% of the study device is used in the study. The non-inferiority margin  $\delta$  of -0.033 is chosen in the study. 212 subjects are required to achieve  $100(1 - \beta) \% = 80\%$  power to detect non-inferiority at the Significance level of  $\alpha = 0.05$ . To account for 10% lost to follow-up, the total number of additional subjects is 237. Therefore, the estimated enrolment for the study will be 387 subjects.

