## 7.2 Analysis Populations

The following subject populations will be used for the statistical analysis of this study.

- **Full analysis set population (FAS)**, following Intention to Treat principle including all subjects who are enrolled into the study.
- **Per-Protocol Population (PP)**, including all subjects in the full analysis set who have no significant protocol deviations and met the inclusion/exclusion criteria.
- **Per-Protocol Population 1(PP1)**, including all subjects in the full analysis set who have no significant protocol deviations and met the inclusion/exclusion criteria. This is the original cohort of subjects in the study who were enrolled prior to the additional proof testing and improvements in device inspection process. This population will be used for supporting analysis of the primary endpoint.
- **Per-Protocol Population 2(PP2)**, including all subjects in the full analysis set who have no significant protocol deviations and met the inclusion/exclusion criteria. This is the additional cohort of subjects who were enrolled after the additional proof testing and improvements in device inspection process. This population will be used for supporting analysis of the primary endpoint.

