## 7.3 Handling of Missing, Incomplete and Repeat Data

Data will be analysed as observed in the study database.

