# Statistical Analysis Plan

A Multi-center Outcomes Clinical Study of the PyroTITAN™ HRA Shoulder Implant in Humeral Head Resurfacing

Number: CP-HRA-002  
ST: ST1159  
Version: 1.0 05/Oct/2023  
Page: 9 of 19

- Binary variable for clinical success (device survival), 1 if all the following are true and 0 if any is false:
  - A. Device remains implanted.
  - B. Absence of device-related complications requiring surgical replacement, removal, or augmentation of components.
  - C. Freedom from chronic dislocation.

A will be determined through absence of a removal/ revision

B will be determined through assessment of complications forms

C will be determined through assessment of Adverse Events

- Duration to intervention = Date of surgical intervention – Date of surgery

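### The 10-year non-inferiority decision uses a 1/0 success proportion with no rule for subjects of unknown 10-year status, while the censoring rule belongs to a Kaplan-Meier analysis that is only conditional

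*SAP*

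**What the plan says.** SAP 7.9 defines clinical success as 1 if components A, B and C all hold and 0 otherwise, and makes the 10-year rate the primary endpoint. On the estimate: "The survival rate (the clinical success rate) will be calculated and the associated 95% exact confidence interval presented". The threshold is 96.1 − 3.3 = 92.8%. The 2- and 5-year rates use the same estimator. The primary population is the FAS, which SAP 7.2 defines as "including all subjects who are enrolled into the study".

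Three passages bear on a subject whose 10-year status is unknown:

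- SAP 7.4, on component A: "A will be determined through absence of a removal/ revision". Components B and C come from complication forms and adverse events. None of the three requires 120-month follow-up.
- SAP 7.3: "Data will be analysed as observed in the study database". Nothing else stands in that section, although the EQ-5D text in 7.4 refers to it for an LOCF rule.
- SAP 7.9, after the decision rule: "If data allows, time-to-event curves for device survival will be estimated using the Kaplan-Meier technique". The next sentence gives the censoring rule: "those lost to follow up or withdrawn from the study for reasons other than device revision or removal will be regarded as censored observations".

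SAP 6.1 expects loss. For the original 150 subjects it says "With an expected attrition rate of 10% per annum". For the added cohort it says "To account for 10% lost to follow-up", which takes 212 to 237. Under Protocol 6.5, subjects who withdraw but keep the implant need no further follow-up. Under Protocol 8.0, lost subjects are not counted as withdrawn. Under Protocol 7.0, subjects whose implant is removed are withdrawn.

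**The concern.** A 1/0 variable has no state for unknown, and an exact interval for a proportion needs a numerator and a denominator. The SAP fixes neither for subjects with unknown status. At least three readings are compatible with the text:

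1. **Lost = success.** Component A is set by the absence of a recorded removal or revision, so a subject lost at year 2 with no event form scores 1. The rate is biased upwards.
2. **Lost dropped.** As observed means known status only. Early failures stay in, while event-free subjects who are lost leave the denominator. The rate is biased downwards.
3. **120-month attendees only.** Revised subjects have already been withdrawn, so the rate tends towards 100%.

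The censoring rule does not choose between these, because a simple proportion cannot hold censored observations. The choice is therefore left until the data are in hand, and it can decide the primary conclusion. The same gap affects the 2- and 5-year results, which SAP 7.14 says are to be published.

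**Working it through.** **Inputs.** From SAP 6.1 and 7.9: N = 387 (150 + 237); reference 96.1%; margin 3.3 points; loss of 10% per annum in the 150 and 10% in the 237. Assumptions that are not in the plan: the second 10% is the total over 10 years; failure and loss hazards are constant; loss is independent of failure. The pass rule is a lower two-sided 95% limit above 92.8%, which follows from the difference criterion in 7.9. A later sentence in 7.9 uses the upper limit; that is a separate defect.

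**The plan's own figures.**
- 150 × 0.9^10 = 52.3, as stated.
- 0.961 × 0.039 × (1.645 + 0.842)² / 0.033² = 212.8, against the stated 212 (this fits one-sided α = 0.05); 213/0.9 = 236.7, i.e. 237.
- Retained at 10 years, ignoring failure: 52.3 + 237 × 0.9 = 265.6 of 387, so 31% are lost.

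**Expected counts.** With true 10-year success S, λ = −ln(S)/10. The loss hazard is μ = −ln(0.9) for the 150 and −ln(0.9)/10 for the 237. Per subject:

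- recorded failure: f = λ/(λ+μ) × (1 − exp(−10(λ+μ)))
- known success: r = exp(−10(λ+μ))

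For S = 92.8%: f = 0.0448 and 0.0684, r = 0.3236 and 0.8352.
- Failures F = 150 × 0.0448 + 237 × 0.0684 = 22.9
- Known successes R = 150 × 0.3236 + 237 × 0.8352 = 246.5
- Unknown = 387 − 22.9 − 246.5 = 117.6

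The same data then read:
- lost = success: 1 − 22.9/387 = 94.1%
- lost dropped: 246.5/(246.5 + 22.9) = 91.5%
- lost = failure: 246.5/387 = 63.7%

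For S = 96.1%: F = 12.4 and R = 255.2, giving 96.8%, 95.4% and 66.0%.

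**Chance of passing.** With n = 387, the Clopper-Pearson lower limit exceeds 92.8% with 17 failures (93.06%) but not with 18 (92.75%). With complete follow-up, P(Bin(387, 0.072) ≤ 17) = 1.6% and P(Bin(387, 0.039) ≤ 17) = 74%. For lost = success, the failure count is the sum of two binomials, Bin(150, f₁) + Bin(237, f₂); the chance that it is at most 17 is 11.8% at 92.8% and 92.4% at 96.1%. The lost-dropped and Kaplan-Meier rows come from simulation (4,000 replicates; log-log limits for Kaplan-Meier).

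| Rule, attrition as stated | Reads at true 92.8% | Passes | Reads at true 96.1% | Passes |
|---|---|---|---|---|
| Complete follow-up | 92.8% | 1.6% | 96.1% | 74% |
| Lost = success | 94.1% | 12% | 96.8% | 92% |
| Lost dropped | 91.5% | 0.3% | 95.4% | 35% |
| Kaplan-Meier | 92.8% | 1.7% | 96.1% | 64% |

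The Kaplan-Meier standard error (Greenwood) is 1.09 points at 96.1% and 1.46 points at 92.8%.

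**Range over attrition.**
- *10% in total for all 387.* Lost = success passes 3.0% at a true 92.8%, against 1.8% for Kaplan-Meier. At a true 96.1% the chances are about 81% (lost = success), 65% (lost dropped) and 72% (Kaplan-Meier).
- *10% per annum for all 387* (about 65% lost; an extrapolation that the plan does not make). A true 92.8% reads 95.5% or 87.8%. Lost = success passes 53%, and Kaplan-Meier stays at about 2%. At a true 96.1%, Kaplan-Meier passes about 46%.

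**The case against.** The strongest reply is that a rule exists. SAP 7.9 calls the primary variable device survival, the censoring sentence is itself unconditional, and the words about data allowing it qualify only the curves. A censored 10-year survival rate is then a fair reading. This is partly right: the censoring principle is there and should be kept. But no Kaplan-Meier estimate or interval is linked to 92.8%, and the exact interval on a 1/0 variable, which is linked to it, cannot use censored observations. The SAP says exact without naming the binomial, but that is the natural meaning for a 1/0 variable.

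Three further points temper the size and do not remove the problem:

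- The pass rates use the lower limit. Under the upper-limit sentence in 7.9, nearly everything passes under every reading (at a true 92.8%: 99.9% lost = success, 89% lost dropped, 97% Kaplan-Meier). The bias in the estimate stands either way.
- The attrition figures are planning values from the 2013 protocol. Actual enrolment and loss are not in the documents, and with 10% total loss in everyone the effect is much smaller.
- Protocol 11.1 calls the study exploratory. SAP 7.9 nevertheless sets a formal hypothesis and says when the study counts as successful.

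**Conclusion.** The concern holds and should be fixed before the analysis. The primary decision statistic has no rule for unknown status. A literal reading of the derivation in SAP 7.4 overstates success, and another permitted reading understates it. With the attrition stated for each cohort, the choice between those two moves the chance of passing at a true 96.1% from 35% to 92%. The reading that favours the device multiplies false non-inferiority about sevenfold (11.8/1.6 = 7.4). These sizes rest on constant hazards, independent loss, 387 enrolled, 10% total loss in the added cohort and the lower-limit criterion; they grow or shrink with actual loss. The direction of each bias does not depend on the amount of loss. Kaplan-Meier is unbiased under the same assumptions and keeps the error rate near 2% across the attrition range examined.

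**What to change.** In SAP 7.9, replace the estimator and decision sentences with text such as:

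> The primary estimate is the Kaplan-Meier probability of clinical success at 120 months from surgery in the FAS, reported also at 24 and 60 months. The event is the first failure of A, B or C. Subjects who are lost, die, or withdraw for any other reason are censored at the last contact at which implant status was known. Non-inferiority is concluded if the lower limit of the two-sided 95% confidence interval (log-log) exceeds 92.8%.

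Then:

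- Remove the condition on producing the Kaplan-Meier analysis.
- In SAP 7.4, state that the 1/0 variable is missing, not 1, when no failure is recorded and 120-month status is unknown.
- Keep as sensitivity analyses: the exact interval in subjects of known status; lost = success; lost = failure (a bound only, since it reads about 64% at a true 92.8%); and cumulative incidence of failure with death as a competing event.
- Report the number with unknown status at 24, 60 and 120 months.

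**Cost.** SAP wording and modest programming. The censoring principle (7.9) and the intervention dates (7.4) exist already; the last-contact date and the handling of deaths need to be specified. Kaplan-Meier assumes that censoring is non-informative, which the sensitivity analyses should probe. It does not recover lost information: at a true 96.1% the chance of passing is 64% under the stated attrition, against 74% with complete follow-up. The choice of log-log limits is a convention; any pre-specified interval that suits a rate near 1 would serve.

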# 7 STATISTICAL ANALYSIS

## 7.1 General

Smith + Nephew's Global Biostatistics group will conduct the statistical analysis for this study. Unless otherwise stated, all significance tests and hypothesis testing will be two-sided, performed at the 5% significance level. Resulting p-values will be quoted and 95% two-sided confidence intervals will be generated where appropriate. All p-values will be rounded to three decimal places, p-values less than 0.001 will be presented as '<0.001' in all tables.

Where data summaries are specified, categorical and ordinal variables will be summarized with frequencies and percentages. Continuous variables will be summarized with the following summary statistics: number of observations, mean, median, standard deviation, minimum and maximum values. All analyses will be performed in SAS 9.4 (or later).

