### 7.9 Analysis of Primary Endpoint(s)

A composite endpoint for Clinical success (device survival) is defined as a binary variable (1/0) (1 if all the following are true and 0 if any is false):

- A. Device remains implanted.
- B. Absence of device-related complications requiring surgical replacement, removal, or augmentation of components.
- C. Freedom from chronic dislocation.

The primary endpoint is the clinical success (device survival) rate at 10-years.

The study hypothesis is to test whether the 10-year survival (i.e., clinical success) rate in the investigational PyroTITAN HRA group is non-inferior to the reference rate at 96.1%. This study will be considered successful if the upper bound of the two-sided 95% confidence interval for the success rate difference (reference – study survival rate) is less than the non-inferiority margin of 3.3%.

The primary non-inferiority hypothesis is formulated as:

$$H_0: P_0 - \delta \geq P_T$$

$$H_a: P_0 - \delta < P_T$$

The variables are defined as follows:

$P_T$  = 120-month success rate in the PyroTitan HRA group

$P_0$  = Reference success rate from original population

$H_0$  = Null hypothesis

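### SAP 7.9 tests the wrong confidence limit: non-inferiority is concluded when the upper, not the lower, 95% limit of the success rate exceeds 92.8%

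*SAP*

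**What the plan says.** SAP Section 7.9 sets the hypotheses as H0: P0 − δ ≥ PT against Ha: P0 − δ < PT. PT is the 120-month success rate and P0 the reference rate. The aim is to show that the device "is non-inferior to the reference rate at 96.1"%, and δ is given as "Non-inferiority margin pre-specified to be 3.3"%. The boundary is therefore 92.8%.

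The section then gives two operating rules.

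- **Difference scale.** "This study will be considered successful if the upper bound of the two-sided 95% confidence interval for the success rate difference", taken as reference minus study, is below 3.3%.
- **Rate scale.** The success rate is to be calculated and "the associated 95% exact confidence interval presented". The rule that follows is: "If the upper 95% confidence limit is greater than the reference rate minus the non-inferiority margin", worked out there as 92.8%, non-inferiority can be concluded.

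SAP Section 7.1 adds that "all significance tests and hypothesis testing will be two-sided, performed at the 5% significance level" unless otherwise stated. Protocol Section 11.3 gives the margin and the sample size but no confidence-limit rule, so it does not settle which version applies.

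**The concern.** Both rules refer to an upper limit, but the two scales run in opposite directions. On the reference-minus-study scale a large value is bad, so the upper bound is the one to control. On the success-rate scale a large value is good, so the lower limit is the one that must clear the boundary. The word upper was probably carried from one scale to the other.

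The rate-scale sentence directly follows the exact interval that will be computed and carries the worked threshold, so a programmer could well code it literally. Applied that way, it reverses the burden of proof: the device passes unless it is shown to be worse than 92.8%. It also becomes easier to meet as subjects are lost, because a wider interval has a higher upper limit. Since the SAP does not rank the rules, a result falling between the two thresholds could be reported either way after the data are seen.

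**Working it through.** **Inputs.** Reference 96.1%, margin 3.3 points and an exact 95% interval (SAP 7.9); two-sided 5% level (SAP 7.1); 212 evaluable, 237 additional and 387 total subjects, with 10% per annum attrition for the original cohort (SAP 6.1, Protocol 11.3). The exact interval is taken as two-sided Clopper-Pearson.

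**Step 1: the plan's own sample size.** The one-sample normal approximation is n = p(1 − p)(z₁₋α + z₀.₈₀)² / δ², with p = 0.961 and δ = 0.033. At one-sided α = 0.05 it gives 0.961 × 0.039 × (1.645 + 0.842)² / 0.033² = 212.8, which agrees with the stated 212; 213 / 0.9 rounds up to 237. The plan's inputs are therefore read as intended: a single-sample test against a fixed 96.1%.

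**Step 2: put both rules on one scale.** Let L and U be the limits for PT. With the reference fixed at 0.961, the upper bound for reference minus study is 0.961 − L. Then

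- difference rule: 0.961 − L < 0.033, which is L > 0.928;
- rate rule as written: U > 0.928.

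Only the first rejects H0: PT ≤ 0.928.

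**Step 3: pass thresholds.** For each n, find the smallest number of successes whose Clopper-Pearson limit exceeds 0.928. At n = 387:

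- 348 successes: U = 92.7%, fails the written rule;
- 349 successes (90.2%): interval 86.8% to 93.0%, passes the written rule;
- 369 successes: L = 92.75%, fails the lower-limit rule;
- 370 successes (95.6%): L = 93.1%, passes the lower-limit rule.

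Results from 349 to 369 successes therefore pass one rule and fail the other. At n = 212 the conflicting range is 189 to 204.

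**Step 4: pass probabilities.** These are P(X ≥ threshold) for X ~ Binomial(n, p). The evaluable number at ten years is not given, so a range is shown. The value 135 is 387 × 0.9¹⁰ = 134.9, which assumes that the original cohort's attrition applies to everyone; 52 is the plan's own ten-year figure for the original 150.

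| n | Threshold, upper rule | Pass at true 92.8% | Pass at true 90% | Threshold, lower rule | Pass at true 92.8% |
|---|---|---|---|---|---|
| 387 | 349 (90.2%) | 97.8% | 50% | 370 (95.6%) | 1.6% |
| 237 | 212 (89.5%) | 97.8% | 66% | 228 (96.2%) | 2.2% |
| 212 | 189 (89.2%) | 98.1% | 71% | 205 (96.7%) | 1.3% |
| 135 | 119 (88.1%) | 98.3% | 81% | 132 (97.8%) | 1.1% |
| 52 | 44 (84.6%) | 98.9% | 93% | 52 (100%) | 2.1% |

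The type I error of the written rule is about 98% at every n. The observed rate that is enough to pass falls from 90.2% to 84.6% as n shrinks.

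**The case against.** The best defence is that the only sentence saying when the study counts as successful is the difference-scale one. That sentence is correct, and so is the direction of H0 and Ha. On that reading the rate-scale sentence is a slip in a restatement, and the 98% arises only if someone follows it in preference to the rest of the section. This stands as a matter of framing: the defect is an internal contradiction, and the error rate is conditional on which sentence is applied. It does not make the sentence harmless, because the SAP gives no order of precedence and the faulty sentence is the one tied to the interval to be computed.

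Three smaller points also have force.

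- The written rule does not pass data that prove inferiority to the boundary; at 349/387 the interval still includes 92.8%. What it drops is the requirement to prove non-inferiority.
- The two rules coincide after correction only if 96.1% is a constant. Section 7.9 tests against 96.1% but also describes P0 as coming from the original population, which is an estimate.
- The protocol calls the study exploratory (Sections 11.1 and 11.6). That lowers the stakes but does not excuse the rule, since both documents plan a formal non-inferiority test.

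**Conclusion.** The concern holds. The rate-scale rule in SAP 7.9 uses the wrong limit, and it contradicts both the hypotheses and the difference rule in the same section. If it is followed, a device exactly at the non-inferiority boundary passes about 98% of the time instead of at most 2.5%, and a device with a true rate of 90% passes 50% of the time at n = 387, 71% at n = 212 and 81% at n = 135. No choice of alpha level or interval method makes an upper limit above 92.8% evidence for Ha.

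The figures assume a fixed reference, a simple binomial outcome without censoring, and Clopper-Pearson limits. The evaluable n at ten years is unknown, but the 98% hardly changes across the range shown. This must be corrected before the primary analysis, because it concerns the formal test of the primary endpoint.

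**What to change.** In SAP 7.9, replace the rate-scale sentence with: *If the lower limit of the two-sided 95% exact confidence interval for the success rate is greater than 92.8%, non-inferiority is concluded.* Add that the reference is held fixed at 96.1%, and that this is the same criterion as the rule for the reference-minus-study difference, evaluated with the same exact interval.

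The cost is one changed word and a clarifying sentence, with no change to data, design or resources. The team should know one thing when making it. Under the lower-limit rule, power at a true 96.1% is about 41% at n = 212, 55% at n = 237 and 74% at n = 387, below the 80% stated in the sample size section. The correction does not cause this. The difference rule already implies it, and the stated 212 reproduces only with a one-sided 5% level and a normal approximation.

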#### **5.4 Screening / Enrollment**

The surgeon will recommend whether the patient should be implanted with this device even if the patient decides not to take part in the study.

The patient must be screened against the inclusion and exclusion criteria (Section 5.3). Where a subject fails to fulfill any element of the inclusion and exclusion criteria, this will be documented. The subject will not be advanced any further into this investigation. Screened Subjects who meet all eligibility criteria and consent to participation must be entered into the study.

The subject will only be allocated to the next available investigational subject number when it is confirmed that the subject is eligible and the procedure will ensue. This number will consist of the center study number followed by 001 for the first patient, 002 for the second patient and so on, (e.g. 2001 site 2 subject 1). This number will then become the unique identifier of the subject and will be written on each page of the CRF and all other study documentation relating to that subject. A master subject list which will be kept strictly confidential and will not be removed from the Investigational Site will record the full name, subject number and clinic record number for each enrolled subject.

Any subject who wishes to withdraw from this investigation on his/her own accord and for whatever reason is entitled to do so without obligation and prejudice to further treatment. In addition, the Investigator may decide for reasons of medical prudence, to withdraw a subject. In either event, the Investigator will clearly document the date and reason(s) for the subject's withdrawal from this investigation in the clinic notes and should indicate whether or not he considers it related to the device.

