### Post-Operative Withdrawal

Subjects withdrawn from the study post-operatively (e.g., withdrawal of consent, etc.) who maintain the investigational components do not require continued follow-up in accordance with the study protocol. However, all data obtained up until the time of consent withdrawal will be available for analysis. The Withdrawal CRF must be sent to the Sponsor.

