## **7.0 Revision/Re-operation**

---

Post-operative surgical procedures associated with the operative shoulder are categorized as Adverse Events. If a Subject undergoes any surgical procedure on the operative shoulder in which all of the original Pyro-Titan Resurfacing Shoulder implant components are retained (debridement etc), the Subject is not withdrawn from the study and all follow-up visits are maintained according to the Subject Management Schedule. If the Pyro-Titan Resurfacing Shoulder prosthesis implant is removed then the Subject is considered revised, is withdrawn from the study, an Adverse Event and Study Completion CRFs must

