## **10.0 Termination of Subject Participation**

---

Any subject who wishes to withdraw from this clinical investigation on his/her own accord and for whatever reason is entitled to do so without obligation and prejudice to further treatment. In addition, the Clinical Investigator may decide for reasons of medical prudence (e.g. stroke, amputation), to withdraw a subject. In either event, the Clinical Investigator will clearly document the date and reason(s) for the withdrawal on the Withdrawal CRF. The investigator should note if the withdrawal was related to the device.

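### Withdrawals recorded as device-related with the implant retained are failures in no planned analysis, and the Kaplan-Meier censoring exception is narrower than the composite endpoint

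*SAP*

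**What the plan says.** **What is collected.** Protocol 10.0 asks for the date and reason of each withdrawal on the Withdrawal CRF and adds: "The investigator should note if the withdrawal was related to the device". Protocol 5.4, repeated in 22.0, places the documentation in the clinic notes and says that the investigator "should indicate whether or not he considers it related to the device".

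**What happens after withdrawal.** Under Protocol 6.5, subjects withdrawn after surgery "who maintain the investigational components do not require continued follow-up in accordance with the study protocol". Under Protocol 7.0, if the "implant is removed then the Subject is considered revised, is withdrawn from the study".

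**What is analysed.** SAP 7.4 and 7.9 define success as three conditions that must all hold: (A) the device is still implanted, (B) there has been no device-related complication needing components to be replaced, removed or augmented, and (C) there is no chronic dislocation. For the 10-year rate, SAP 7.9 says: "The survival rate (the clinical success rate) will be calculated and the associated 95% exact confidence interval presented". It then adds: "If data allows, time-to-event curves for device survival will be estimated using the Kaplan-Meier technique". The censoring rule follows directly: "those lost to follow up or withdrawn from the study for reasons other than device revision or removal will be regarded as censored observations". SAP 7.3 says only: "Data will be analysed as observed in the study database".

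**The concern.** Censoring in a Kaplan-Meier analysis assumes that those who leave have the same later failure risk as those who stay. A withdrawal that the investigator has attributed to the device is recorded evidence against that assumption. Because follow-up then ends, a later revision elsewhere need not reach the database. The expected direction of error favours the implant, and the margin is only 3.3 points.

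There is also a mismatch inside SAP 7.9. The exception to censoring names revision and removal only, whereas the composite can also fail through augmentation (B) or chronic dislocation (C) with the implant in place. Protocol 7.0 calls a subject revised when the implant is removed, so neither case is clearly a revision.

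**Working it through.** **The plan's own figures.** With reference rate 0.961, margin 0.033, one-sided alpha 0.05 and 80% power, n = 0.961 × 0.039 × (1.645 + 0.842)² / 0.033² = 212.8. The plan states 212. Then 213 / 0.9 = 236.7, so 237, and 150 + 237 = 387. Attrition in the original cohort: 150 × 0.9^10 = 52.3. These reproduce and are not in dispute.

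**How each kind of leaver is treated**

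- Withdrawn for revision or removal: not censored, and fails A.
- Withdrawn after chronic dislocation, or after augmentation, with the implant retained: fails C or B under SAP 7.4, but is censored under the literal rule in 7.9. The only time variable in the primary-endpoint derivations runs to a surgical intervention, so a dislocation managed without surgery has no event date.
- Withdrawn for another device-related reason with the implant retained: censored in the Kaplan-Meier analysis. In the proportion, the subject either drops out of the denominator or, having no recorded removal, counts as a success. Neither counts against the device.

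**Size in the Kaplan-Meier estimate.** Inputs: a 10-year estimate of 96.1%, 387 subjects, and the two loss figures in SAP 6.1 (10% per year, stated for the original cohort; 10% in total, used for the new cohort). The share s of leavers who are device-related withdrawals with the device retained is not in the documents, so 1%, 2% and 5% are assumed. With constant hazards, counting that share as events gives:

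- 10% per year: S(10) = 0.961 × 0.9^(10s)
- 10% in total: S(10) = 0.961 × 0.9^s

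Under yearly attrition the model expects about 248 of 387 to leave before failing, so s × 248 events are added.

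| s | Events added (10% per year) | Estimate (fall), 10% per year | Estimate (fall), 10% in total |
|---|---|---|---|
| 1% | 2.5 | 95.1% (1.0) | 96.0% (0.1) |
| 2% | 5.0 | 94.1% (2.0) | 95.9% (0.2) |
| 5% | 12.4 | 91.2% (4.9) | 95.6% (0.5) |

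The point estimate reaches 92.8% when s = ln(0.961/0.928) / (−10 ln 0.9) = 0.033, or about 8 subjects under yearly attrition. Under 10% total loss it takes s = 0.33.

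**Size in the 10-year proportion.** Under yearly attrition, 387 × 0.9^10 = 135 remain and 252 have gone. The result depends on how the missing rule is filled in:

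- *Observed subjects only.* With 5 failures (135 × 0.039 = 5.3), the rate is 130/135 = 96.3% (exact 95% CI 91.6 to 98.8). Adding 5 leavers as failures (2% of 252) gives 130/140 = 92.9% (87.3 to 96.5). Adding 13 (5%) gives 130/148 = 87.8% (81.5 to 92.6). This exaggerates the effect, because the other leavers stay outside the denominator.
- *All 387, with no recorded failure taken as success.* Each reclassified subject moves the rate by 1/387 = 0.26 points, so 5 move it by 1.3 points and 13 by 3.4.

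**The case against.** Several points on the other side stand.

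- A reader might infer that anyone who leaves because of the implant escapes the analysis. The documents do not support this: withdrawal for revision or removal is exempt from censoring and fails component A.
- A reader might infer that the censoring rule governs the non-inferiority decision. It sits with the Kaplan-Meier curves, which are made only if data allow. The decision uses the exact interval, where the fault is a missing rule and not a stated one.
- SAP 7.9 equates device survival with the composite, so an analyst could take B and C failures as events before applying censoring. That is sensible, but the exception does not say it.
- Leaving with the implant in place is not itself a composite failure. Pain or dissatisfaction with a retained device is outside A, B and C, so censoring such subjects in the main analysis is ordinary practice.
- Some visibility exists. SAP 7.6 summarises reasons for study completion, and the adverse event listing in 7.12 shows device relationship and whether participation stopped because of the event. Neither enters the primary endpoint.
- The shares above apply to all leavers, but Protocol 8.0 does not regard lost-to-follow-up subjects as withdrawn. They carry no relatedness note, so the proposed analysis can reach only formal withdrawals.

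A further tempting reading is that a few subjects decide the trial. If all 387 were evaluable, about 15 failures would be expected (387 × 0.039), and the exact lower limit stays above 92.8% up to 17, so three more would reverse the result. That assumes nobody left, in which case there are no device-related leavers. With 135 evaluable, an on-target result already has a lower limit of 91.6%, so there is no pass to reverse.

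**Conclusion.** The point holds as a gap in the handling of withdrawals, in two parts. First, the censoring exception does not match the composite: read literally, it censors subjects who have already failed B or C. This follows from the text and needs no assumption. Second, the protocol asks for device-relatedness at withdrawal, but no planned analysis uses it to test the primary result, and follow-up ends for those who keep the implant.

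The size cannot be fixed from the documents. For assumed shares of 1% to 5% of leavers, the fall in the 10-year Kaplan-Meier estimate is at most about 1.0 to 4.9 points under 10% yearly attrition, and about 0.1 to 0.5 points under 10% total loss. These are worst-case bounds that treat every such subject as a failure. They do not show that reported survival will be too high; the direction is expected, not proven.

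**What to change.** 1. In SAP 7.9, extend the exception to all three components, so that any subject who meets an A, B or C failure at or before withdrawal is an event. Define the event date for a chronic dislocation managed without surgery.
2. In SAP 7.9, state how withdrawals enter the 10-year proportion.
3. Pre-specify one sensitivity analysis, for both the Kaplan-Meier estimate and the proportion, that counts withdrawals recorded as device-related with the device retained as failures (in the Kaplan-Meier version, on the withdrawal date). Tabulate their number by cohort and report the analysis beside the primary result, without making it a second success criterion: it rests on a subjective judgement in an unblinded study.

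The cost is a few sentences and one re-run if the relation is coded in the database. The case report forms are not available here, and Protocol 5.4 and 22.0 point to the clinic notes, so the item may have to be retrieved from source. The downside is that some counted failures will not be true failures, which is why this belongs in a sensitivity analysis.
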